### 10.3 Analysis of Deaths

Survival curves will be produced using the Kaplan-Meier product limit estimator. Survival will be tracked through registry completion at the one-year follow-up visit. In addition, 95% confidence intervals for the Kaplan-Meier survival curves will be computed and plotted at monthly time intervals.

A frequency table will also be presented containing one-year mortality rates, along with 95% two-sided binomial proportion confidence intervals using a normal approximation to the binomial.

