### SCHEDULE OF ASSESSMENTS

Assessment	Admission Evaluation	Immediate Post-Procedure	Discharge	One Year Follow-Up*
History	√			
Modified Rankin Scale**	√			√
Hunt and Hess +	√			
Aneurysm Occlusion		√		√
Procedural Data Points ++		√		
Adverse Events		√	√	√

\* Single follow-up visit to be conducted in accordance to the standard of care at the participating hospital. Period for which to capture follow-up visit is within one year  $\pm 6$  months

\*\* Only for patients in which mRS would be captured as standard of care

+ Required for patients with SAH only

++ Proportion of SMART coils implanted, target location access attempts, radiation exposure, coiling start/end time

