## **12 Lost to Follow-Up and Missing Data**

Missing data are expected to arise on subjects who discontinue the registry early. For sensitivity purposes, the following additional analyses will be conducted on the primary efficacy endpoint:

- Analyze only subjects with complete one-year retreatment rate data
- For those subjects without any observations after treatment, missing one-year retreatment rate data will be imputed from baseline scores and included in an analysis

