## Subject Deaths

| Subject Deaths      | All Subjects (N = N) | 95% CI       |
|---------------------|----------------------|--------------|
| One-Year Death Rate | X.X% (n/N)           | (X.X%, X.X%) |

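### The one-year mortality rate is planned as a simple binomial proportion, although follow-up ends anywhere from 6 to 18 months and losses are expected, so in general it does not estimate one-year risk.

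*SAP*

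**What the plan says.** SAP 10.3 plans two summaries of death.

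- The first is a survival analysis: "Survival curves will be produced using the Kaplan-Meier product limit estimator". Confidence intervals are plotted monthly, and SAP 14 runs the figure up to one year.
- The second is a table: "A frequency table will also be presented containing one-year mortality rates", with "95% two-sided binomial proportion confidence intervals using a normal approximation to the binomial". Its shell in the SAP appendix (Subject Deaths) is one row, "One-Year Death Rate", shown as n/N under an all-subjects column.

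The end of observation is a visit, not a fixed day: "Survival will be tracked through registry completion at the one-year follow-up visit". The Schedule of Assessments in Protocol section 4 describes that visit as follows: "Single follow-up visit to be conducted in accordance to the standard of care at the participating hospital". The window is wide: "Period for which to capture follow-up visit is within one year" plus or minus 6 months. No other contact after discharge is scheduled.

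Incomplete follow-up is foreseen. SAP 7 lists loss to follow-up and withdrawal among the reasons for discontinuation, and SAP 12 states: "Missing data are expected to arise on subjects who discontinue the registry early". The extra analyses in the text of SAP 12 are for the primary efficacy endpoint only, and the sensitivity shell has no row for death.

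No passage says whether the numerator of the death rate stops at 12 months, or how a subject who leaves alive before 12 months, or is lost, enters the denominator.

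**The concern.** A binomial proportion estimates one-year risk only if every subject is observed, dead or alive, for one year. Here planned exit ranges from 6 to 18 months and some subjects leave earlier. Neither simple denominator repairs this.

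- **All subjects.** Anyone who exits alive at month 7, or is lost at month 2, is treated as a one-year survivor. Unless the numerator is cut at 12 months, a death at month 15 may be counted.
- **Subjects with known status.** A death settles a subject's status, whereas survivors who are lost drop out of the denominator. This pushes the rate up.

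The Kaplan-Meier curve in the same section handles unequal follow-up by censoring. The report could therefore carry two different one-year mortality figures, with no rule on which one stands. The direction of the error in the tabulated figure would depend on a denominator that is not specified, so a reader could not correct for it.

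**Working it through.** The documents state no mortality figure, so there is none to reproduce. Everything below except n and the visit window is an assumption.

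**Inputs.** From the documents: n about 1,000 (Protocol 9.1); one exit visit between 0.5 and 1.5 years (Schedule of Assessments). Assumed: true one-year risk 8%, with early-weighted hazard (Weibull, shape 0.5); visits uniform over the window; a fraction L of subjects with a loss time uniform over the first 6 months, unrelated to risk of death.

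**Step 1, risk curve.** F(t) = 1 − exp(−λ√t), with λ = −ln(0.92) = 0.0834. Hence F(0.5) = 5.73%, F(1) = 8.00%, F(1.5) = 9.71%.

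**Step 2, deaths before exit, by type of subject.**
- Not lost: average of F over 0.5 to 1.5 years, by Simpson's rule (5.73 + 4 × 8.00 + 9.71)/6 = 7.91%.
- Lost: average of F over 0 to 0.5 years, λ × (2/3) × √0.5 − (λ²/2) × 0.25 = 3.93% − 0.09% = 3.84%.

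**Step 3, the two crude rates.**
- Deaths/all = (1 − L) × 7.91% + L × 3.84%.
- Deaths/known = that figure divided by (1 − L × 0.9616), since 96.16% of the lost leave alive.

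| Lost (L) | Deaths/all | Deaths/known | True risk |
|---|---|---|---|
| 0% | 7.9% | 7.9% | 8.0% |
| 10% | 7.5% | 7.50/0.9038 = 8.3% | 8.0% |
| 20% | 7.1% | 7.10/0.8077 = 8.8% | 8.0% |
| 30% | 6.7% | 6.69/0.7115 = 9.4% | 8.0% |

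Simulation of the same set-up agrees to about 0.1 point (6.6% to 6.7% and 9.3% to 9.4% at 30% loss) and gives about 8.0% for Kaplan-Meier at 12 months throughout.

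**Step 4, scale.** The 95% half-width at 8% is 1.96 × √(0.08 × 0.92/1000) = ±1.7 points. The largest gap in the table is 9.4 − 8.0 = 1.4 points.

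**Step 5, sensitivity to visit timing.** If all visits fall between 6 and 12 months, deaths/all is 6.6% at 10% loss and 6.0% at 30%; the gap of 2.0 points at 30% loss exceeds the half-width.

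A second simulation assumed a 5% true risk, for which the half-width is ±1.35 points. Deaths by exit over all subjects ranged from 3.8% (early-weighted visits, 20% lost) to 5.9% (late-weighted visits, none lost), so the sign can go either way. Cutting the numerator at 12 months while keeping all subjects in the denominator does not cure it: uniform visits and no loss gave 4.35% to 4.87%, against about 5.0% by Kaplan-Meier.

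**Step 6, can Kaplan-Meier deliver the 12-month figure?** At 8% risk with uniform visits, the share still at risk at 12 months is 0.5 × 0.92 = 46% with no loss and 0.5 × 0.70 × 0.92 = 32% with 30% loss, which is ample at n = 1,000. If all visits fall by 12 months, virtually no one is at risk at day 365. In the extreme where every visit is at 6 months, a Kaplan-Meier curve carried flat to 12 months gave only 2.5% to 3.8% for a true 5%.

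**The case against.** The case for leaving the plan alone has four parts.

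- **Kaplan-Meier is already planned.** It comes first in SAP 10.3, with intervals, and its figure runs to one year; the table is an addition. This stands, and it is why the fix is cheap. It does not tell the reader which figure is the one-year rate.
- **'One-year' may only be the name of the visit.** The documents use it that way elsewhere, for example for the follow-up modified Rankin score, so the row could mean mortality through that visit. That is possible. The figure would then cover unequal periods, and the label would still mislead.
- **The effect may be tiny.** With visits symmetric about 12 months and no loss, the all-subjects rate is 7.9% against 8.0%. This stands, but the agreement comes from early and late exits offsetting each other, not from the method.
- **Kaplan-Meier is not assumption-free.** It needs non-informative exit and subjects at risk at 12 months. The simulations build the first in, so its 8.0% is expected by construction. This stands and shapes the fix.

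A reader might infer more than the documents support. They do not make mortality a headline result: death is neither a primary nor a secondary endpoint, and the sample size does not rest on it. They do not say that a 6-month exit counts as a one-year survivor or that a month-15 death counts as a one-year death; the rule is undefined, and dates of death are listed, so a day-365 cut-off is possible. Nor do they show that the two figures will conflict, only that they can. Nothing here shows that the normal approximation itself fails for a rate of this order at n = 1,000.

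**Conclusion.** The point holds in a limited form. The planned proportion does not in general estimate one-year risk and can differ from the Kaplan-Meier estimate beside it. Under the 8% assumptions the error runs from about 0.1 point with no loss to 1.3 points low or 1.4 points high at 30% loss, depending on the denominator. These gaps are inside the ±1.7-point half-width; early-clustered visits combined with loss can push them beyond it. The real size cannot be known from the documents, because mortality, loss and visit timing are not given. The correction is minor to moderate: it concerns a supporting safety summary and leaves the primary and secondary endpoints untouched.

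**What to change.** In SAP 10.3 and the Subject Deaths shell:

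1. Define one-year mortality as 1 minus the planned Kaplan-Meier estimate at 12 months, with its 95% interval and the number at risk. Any standard interval for the Kaplan-Meier estimate will do.
2. Censor at the last date known alive, and state its source. The disposition listing shows a date only for completers, so the source for discontinued subjects needs naming.
3. Set in advance a minimum number at risk at 12 months. If it is not met, report the estimate at an earlier time with adequate numbers, labelled with that time.
4. If a crude count is kept, label it 'deaths observed through registry exit' and give its denominator and the follow-up duration.

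The cost is a small change of SAP wording and one table shell, with no new visits, since the Kaplan-Meier analysis is already planned and dates of death are already listed. The remaining weakness is the assumption that exit is unrelated to risk of death, which the report should state.

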## **11 Pooling Across Centers**

To assess the validity of data pooling, heterogeneity across sites will be examined using relevant methods, such as ANOVA (continuous variables), contingency tables or binary logistic regression (categorical variables), or Cox proportional hazards (event time variables). Any sites containing fewer than ten subjects will be aggregated in this analysis.

All sites will conduct the registry according to a common protocol. Monitoring efforts will be allocated to assess whether sites are adhering to the protocol in a standardized manner to minimize the presence of heterogeneity across centers.

## **12 Lost to Follow-Up and Missing Data**

Missing data are expected to arise on subjects who discontinue the registry early. For sensitivity purposes, the following additional analyses will be conducted on the primary efficacy endpoint:

- Analyze only subjects with complete one-year retreatment rate data
- For those subjects without any observations after treatment, missing one-year retreatment rate data will be imputed from baseline scores and included in an analysis

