## 9.2 General Statistical Methods

This registry is a single-treatment design. Hence, descriptive statistics will provide a basis for the majority of the analyses with a 95% two-sided confidence interval presented. For binary outcomes, the 95% two-sided confidence intervals will be calculated using binomial intervals. For numeric measures, a confidence bound for the mean or mean change from admission will be constructed.

Summary tables (descriptive statistics and/or frequency tables) will be provided for all baseline variables, effectiveness variables, and safety variables, as appropriate. Continuous variables will be summarized with descriptive statistics (n, mean, standard deviation, range, and median). Frequency counts and percentage of patients within each category will be provided for categorical data.

Results collected at multiple visits will be summarized at each visit for which they are collected. Summaries for all measures will include all observed data for each visit.

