## 5 Statistical Methods

For this single-arm registry, results will primarily be presented as descriptive statistics and two-sided 95% confidence intervals.

Baseline, efficacy, and safety variables will be summarized using tables of descriptive statistics for continuous variables (n, mean, median, SD, and range) or frequency counts and percentages for categorical variables.

Confidence intervals will be developed using confidence bounds on the mean or mean change from admission for continuous variables or binomial proportion intervals under a normal approximation to the binomial for categorical variables.

For results developed using data from more than one visit, summaries will be reported for each visit from the full set of observed data available.

Staged procedures are not retreatments for the purposes of running all SMART registry analyses.

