### Sensitivity Analysis

| Sensitivity Analysis  | All Subjects (N = N) | 95% CI |
|--|-----------------------------|---------------|
| Analysis of All Subjects with Follow-Up Complete                      |                             |               |
| Retreatment through Follow-Up  | X.X% (n/N)                  | (X.X%, X.X%)  |
| Adequate Occlusion at Immediate Post-Procedure                               | X.X% (n/N)                  | (X.X%, X.X%)  |
| Re-Access Attempts with Guidewire due to Catheter Kickout (SMART/PC 400/POD) |                             |               |
| 0  | X.X% (n/N)                  | (X.X%, X.X%)  |
| 1  | X.X% (n/N)                  | (X.X%, X.X%)  |
| 2  | X.X% (n/N)                  | (X.X%, X.X%)  |
| ≥ 3  | X.X% (n/N)                  | (X.X%, X.X%)  |
| Procedural Device-Related Serious Adverse Events                             | X.X% (n/N)                  | (X.X%, X.X%)  |
|  |                             |               |
| Analysis of Complete Datasets with Missing Data Imputed               |                             |               |
| Retreatment through Follow-Up  | X.X% (n/N)                  | (X.X%, X.X%)  |
| Adequate Occlusion at Immediate Post-Procedure                               | X.X% (n/N)                  | (X.X%, X.X%)  |
| Re-Access Attempts with Guidewire due to Catheter Kickout (SMART/PC 400/POD) | X.X% (n/N)                  |               |
| 0  | X.X% (n/N)                  | (X.X%, X.X%)  |
| 1  | X.X% (n/N)                  | (X.X%, X.X%)  |
| 2  | X.X% (n/N)                  | (X.X%, X.X%)  |
| ≥ 3  | X.X% (n/N)                  | (X.X%, X.X%)  |
| Procedural Device-Related Serious Adverse Events                             | X.X% (n/N)                  | (X.X%, X.X%)  |

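### SAP 12's sensitivity analyses for one-year retreatment include no pessimistic scenario, and the imputation rule names no score or model that could be applied

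*SAP*

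**What the plan says.** SAP 12 states that "the following additional analyses will be conducted on the primary efficacy endpoint". There are two:

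- The first is a complete-case analysis, worded as "Analyze only subjects with complete one-year retreatment rate data".
- The second is an imputation. The group it covers is introduced with the words "For those subjects without any observations after treatment". The rule that SAP 12 then sets for this group is that "missing one-year retreatment rate data will be imputed from baseline scores and included in an analysis".

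No score, model, imputed value or variance method is given. The mock listing for the primary effectiveness analysis records retreatment as Yes, No or Unknown. SAP 8.1 names the populations (ITT and PP) and the interval method, but not how Unknown is counted.

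The appendix shell headed Sensitivity Analysis has a block titled "Analysis of Complete Datasets with Missing Data Imputed". Besides retreatment it has rows for "Adequate Occlusion at Immediate Post-Procedure", re-access and procedural device-related serious adverse events.

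**The concern.** Retreatment is an event that can happen only after the index procedure, so there is nothing at baseline to carry forward. The admission scores in the protocol's Schedule of Assessments are the modified Rankin Scale, where it is standard of care, and Hunt and Hess, for subarachnoid haemorrhage only. Neither measures retreatment. The SAP 9 variable that separates initial treatment from retreatment at admission describes history, not the outcome.

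Two programmers could follow the sentence and report different rates. More important is what either reading leaves out. Subjects who miss the single standard-of-care follow-up visit may differ in retreatment from those who attend. A sensitivity analysis should show how much worse the lost subjects would have to be before the reported rate changes materially. Neither planned analysis allows lost subjects to be retreated more often than comparable observed subjects.

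**Working it through.** **Inputs.** From SAP 2: p = 8.3% retreatment, N = 1000, two-sided 95% intervals by the normal approximation. Assumed, because the documents give no loss rate: a fraction m = 10%, 20% or 30% with unknown status, and 8.3% retreatment among those of known status.

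**The plan's own figure.** 0.083 ± 1.96 × √(0.083 × 0.917 / 1000) = 6.59% to 10.01%. This matches the stated 6.6% to 10.0%, which therefore takes all 1,000 outcomes as known.

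**Formulas.**
- Complete-case: p, with the interval at n = N(1 − m); call its upper limit U.
- All lost subjects not retreated (the carry-forward reading): p(1 − m), with the interval at N = 1000.
- All lost subjects retreated: p(1 − m) + m.
- Tipping rate, the rate in lost subjects at which the overall rate equals U: (U − p(1 − m)) / m.

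**At m = 20%.**
- Complete-case, n = 800: half-width 1.96 × √(0.083 × 0.917 / 800) = 1.91 points, so 6.39% to 10.21%.
- Not retreated: 0.083 × 0.8 = 6.64%; half-width 1.96 × √(0.0664 × 0.9336 / 1000) = 1.54 points, so 5.10% to 8.18%.
- Retreated: 6.64% + 20% = 26.64%.
- Tipping rate: (10.21 − 6.64) / 0.2 = 17.9%, which is 2.2 times 8.3%.

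| Assumed loss | Complete-case (95% CI) | All not retreated (95% CI) | All retreated | Tipping rate (multiple of 8.3%) |
|---|---|---|---|---|
| 10% | 8.3% (6.5 to 10.1) | 7.5% (5.8 to 9.1) | 17.5% | 26.3% (3.2) |
| 20% | 8.3% (6.4 to 10.2) | 6.6% (5.1 to 8.2) | 26.6% | 17.9% (2.2) |
| 30% | 8.3% (6.3 to 10.3) | 5.8% (4.4 to 7.3) | 35.8% | 15.1% (1.8) |

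Under carry-forward at 20% or 30% loss, the whole interval lies below the complete-case estimate of 8.3%.

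**The prediction reading.** SAP 6 counts lesion evaluation among baseline characteristics, so a model on baseline data is a possible meaning. It could move the rate either way. It would still give lost subjects the same risk as observed subjects with the same baseline data, which is the missing-at-random assumption.

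**Coverage.** The SAP's follow-up visit table and listing contain only the admission evaluation and the follow-up, and the deviations listing treats baseline and procedure as one timepoint. On that footing the rule most naturally covers subjects with no follow-up visit. The protocol's schedule, however, records occlusion and adverse events immediately after the procedure, so read literally the rule would reach almost no implanted subject. If it reached 2% (an assumption), carry-forward would give 0.083 × 0.98 = 8.1%, almost no change.

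**The case against.** This is a descriptive single-arm registry with no performance goal, and the gap lies in a sensitivity analysis. The loss rates above are assumptions, and the all-retreated figures are arithmetic limits rather than forecasts. All of that stands, and it limits the weight of the point.

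Three stronger readings are tempting but are not supported.

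- A reader might infer that the two analyses make the same assumption about lost subjects. Under carry-forward with the wider coverage they do not: one excludes lost subjects and the other counts them as not retreated. On that reading the plan already contains the lower bound, and what is missing is the other side.
- A reader might infer that the complete-case analysis merely repeats the primary, because the protocol says "Summaries for all measures will include all observed data for each visit" and SAP 5 says "summaries will be reported for each visit from the full set of observed data available". Both sentences concern summaries by visit, whereas retreatment is cumulative through follow-up. SAP 12 calls its analyses additional, and the primary shell is headed for all subjects. The denominator is undefined, so duplication is not established.
- A reader might infer that nothing planned compares completers with the rest. The first block of the sensitivity shell reports early outcomes in subjects with complete follow-up, which can be set beside the full-population tables. That is informative about early outcomes, but it does not test informative loss for retreatment.

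**Conclusion.** The point holds. As written, the imputation rule either pushes the rate one way or is an unspecified missing-at-random model, and no planned analysis is pessimistic about lost subjects. At an assumed 20% loss, carry-forward lowers the estimate by 1.7 points (8.3% to 6.6%), about the planned half-width of 1.7 points. At the same loss, a retreatment rate in lost subjects of about 2.2 times the observed one would take the overall rate to the complete-case upper limit, and nothing in the plan would show it.

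These sizes rest on the assumed loss rates, on 8.3% among subjects of known status, and on the rule covering everyone without a follow-up visit. The documents do not show that the primary estimate itself is biased, nor that loss will be large. This should be fixed before the SAP is signed off.

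**What to change.** In SAP 12, replace the second bullet with a rule for all ITT subjects whose one-year retreatment status is unknown. Report:

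1. the rate with all of them counted as not retreated;
2. the rate with all of them counted as retreated;
3. a tipping-point analysis: the retreatment rate in these subjects at which the overall rate reaches the complete-case upper 95% limit. With no performance goal, that limit is a reference only, and the SAP should say so.

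Multiple imputation from the lesion covariates in SAP 9 could be added, with the model named and labelled missing at random. It would not replace items 2 and 3.

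Two minor consistency edits belong with this. SAP 8.1 should state how Unknown and deaths before follow-up enter n/N. For example, if 5% died without retreatment (an assumption) and 8.3% applied to the rest, keeping deaths in N gives 0.083 × 0.95 = 7.9%, and excluding them gives 8.3%. The imputation block of the sensitivity shell should be aligned with SAP 12's restriction to the primary efficacy endpoint.

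The cost is SAP wording and modest programming. The Unknown category, discontinuation reasons and lesion covariates are already planned, so no new data are needed. The bounds will look wide if loss is large.

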## **13 Changes to Planned Analyses**

All changes to this Statistical Analysis Plan (SAP) will be listed in a revised SAP or in the SMART clinical registry report.

